## **10. HUMAN SUBJECTS**

### **Subjects**

50 primary snorers (AHI <15/hr) will be recruited from Queen's Hospital, Romford (Barking, Havering and Redbridge NHS Trust), UK.

Inclusion criteria

- Age 18 years and above (adult population) at entry into study
- Subjects must have a live-in partner as the assessment includes partners report
- More than six month history of habitual snoring (i.e. >5 days per week as reported by partner)

Exclusion criteria

- BMI > 35 kg/m^2
- AHI >15/h, i.e. evidence of moderate to severe OSA from sleep study
- ESS > 10 in participants with AHI 5-15/h (symptomatic mild sleep apnea should be treated with CPAP)
- Symptomatic nasal pathology i.e. septal deviation, nasal polyposis or chronic rhinosinusitis
- Tonsil Hypertrophy (Tonsil size – Grade 3 or greater)
- Tongue or lip piercing
- Pacemaker or implanted medical electrical devices
- Previous oral surgery for snoring
- Relevant facial skeletal abnormalities (i.e. syndromic facial deficiencies, severe micrognathia etc.)
- Oral disease/conditions (see Appendix 3)
- Any criteria that, in the opinion of the investigator, would make the participant unsuitable for the study due to inability to complete required study procedures

#### **11. RECRUITMENT AND PROCEDURES PREPARATORY TO RESEARCH**

Participants will be identified from the sleep clinic at the Department of Otorhinolaryngology, Head and Neck Surgery in Queen’s Hospital, Barking, Havering and Redbridge University Hospitals NHS Trust. Patients may be referred to this service from dental practices.

Participants considered to be suitable for the study will be invited to undergo a 2 night sleep study, performed at home using a WatchPAT device, to determine average AHI. If the AHI is less than 15, the participant will be invited to attend a clinic assessment for upper airway and to undertake an oral assessment.

If all inclusion criteria and none of the exclusion criteria are met, full informed consent will be taken by the Chief Investigator or a delegated member of the research team.

Participants will be on the study for a total of 10 weeks.

#### **12. INFORMED CONSENT**

All informed consent is completely voluntary. Participants and their partners will be given full information regarding the study prior to obtaining consent. Participants will be given the written patient information pack and provided with the full details of the study and its purpose. Participants will be given more than 24 hours to consider their participation in the study and to ask any questions they may have. Participants will be assessed for capacity to consent during the consent process. If lack of capacity is deemed, these participants will not be considered for the study.

#### **13. ALTERNATIVES TO STUDY PARTICIPATION**

Participation will not alter or influence patient’s normal clinical treatment. Participants do not have to take part in the study and if they do decide to, they are able to withdraw at any point.

#### **14. POTENTIAL RISKS**

We believe that this study and the Snoozeal device to be low risk. The investigative tool, the WatchPAT, for the sleep study is routine practice undertaken by thousands of patients and has FDA approval (510K - K161579). The Snoozeal device has been used in a pilot study of 27 patients, which revealed no significant adverse events.

Snoozeal device: The pilot study of the Snoozeal device involved 27 patients who used the device twice daily (double the planned utilization in this trial). The only side effects were feeling tingling of the tongue for a short period (up to 5 minutes) after using the device, excessive saliva production and gum discomfort during use as shown in Table 2. As these symptoms were in keeping with anticipated effects of device use and were not

persistent, we consider this to be a non-significant risk device. The mouthpiece has been modified since the original trial to address any gum contact and discomfort. Compared to RCTs on snoring, quoted in the American Sleep medicine guideline (TheraSnore™), the Snoozeal device has less severe and less prevalent side effects.

A full risk assessment can be found in the DFMEA.

*Table 1: Side effects of the TheraSnore™ appliance (Cooke ME, Battagel JM)*

Side Effect (n = 23)	Non-advanced MAD		Advanced MAD	
	Short term (%)	Long term (%)	Short term (%)	Long term (%)
Muscular discomfort	39	13	74	26
Temporomandibular joint discomfort	26	9	61	22
Abnormal bite on waking	39	9	57	17
Excessive salivation	65	26	65	22
Dry mouth	21	52	26	70

*Table 2: Side effects of the Snoozeal device*

Side Effect (n = 27)	Short term (%)
Tingling sensation	33
Excessive salivation	26
Gum discomfort	19
Feeling of change in speech	4

Sleep Study with WatchPAT:

Participants may experience poorer sleep quality and minor discomfort related to the use of the WatchPAT device due to the larger size (compared to a normal wrist watch) and finger probe. However, we are expecting the level of discomfort to be significantly less when compared with a laboratory based polysomnography. Hypoallergenic tape will be used to minimize risk of skin irritation.

Data Handling: There is a risk of loss of subject confidentiality. This study will comply with the Data Protection Act 1998 and Caldicott Principles as laid out in the privacy and confidentiality considerations below.

**15. RISK MANAGEMENT PROCEDURES AND ADEQUACY OF RESOURCES**

Research Ethics Committee (REC) review & reports

Ethical approval for this study has been granted by Stanmore Research Ethics Committee (REC) using the Integrated Research Application System (IRAS project ID: 219271). All correspondence with the REC will be retained. The Chief Investigator (CI) will notify the REC at the end of the study. It is also the CI's responsibility to produce the final report of the study with the results including any publication and submit to the REC.

Safety reporting

All Adverse Events and Reactions will be logged in data sheet or reported to CI and have cause analysis and assessment performed. If the AE is not defined as serious, the AE will be recorded in the study documents and the participant followed up by the research team. The AE will be documented in the participants' source documents.

Adverse Events (AEs) - any untoward medical occurrence in a participant to whom an intervention has been administered, including occurrences which are not necessarily caused by or related to that intervention. An AE can therefore be any unfavourable or unintended sign (including an abnormal laboratory finding), symptom or disease temporally associated with study activities.

Adverse Reaction (ARs) - any untoward and unintended response in a participant to an intervention. All adverse events judged by either the reporting investigator or the sponsor as having a reasonable causal relationship to the intervention qualify as adverse reactions. The expression 'reasonable causal relationship' means in general that there is evidence or an argument to suggest a causal relationship.

Should any events arise during a therapy session, the session should be terminated immediately. If this does not resolve the issue, the participant should contact the research team, or in case of emergency, seek urgent medical attention.

#### Serious Adverse Events (SAEs)

Serious Adverse Events (SAEs) that are considered to be 'related' and 'unexpected' will be reported to the sponsor within 24 hours of learning of the event, and to the REC within 15 days in line with the required timeframe using the form shown in Appendix 6.

A serious adverse event (SAE) is defined as an untoward occurrence that:

- Results in death,
- Is life-threatening,
- Requires hospitalization or prolongation of existing hospitalization,
- Results in persistent or significant disability or incapacity,
- Consists of a congenital anomaly or birth defect, or
- Is otherwise considered medically significant by the investigator.

SAEs will be reported to the REC where in the opinion of the Chief Investigator the event was serious and:

- Related (it may have resulted from administration of any of the research interventions), and
- Unexpected (the type of event is not listed in the protocol or other Reference Safety Information as an expected occurrence).

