#### Secondary Endpoints:

- A. Reduction in the Epworth Sleepiness Scale (validated hypersomnolence questionnaire) and Pittsburgh Sleep Index (validated sleep quality questionnaire with 7 domains).
- B. Assess safety of device (record and investigate adverse events, oral status and monitor device integrity through use)

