### **See Appendix 1 for endpoint assessment and validation**

#### Safety

- 1) Any side effects or adverse events to be recorded in research record sheets and will be collated for assessment
- 2) Pre and post therapy WatchPat sleep studies will be assessed for change in parameters of saturation and AHI.
- 3) The pre and post oral examination clinical sheets will be scrutinized for any change in oral status.

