## **16. PRIVACY AND CONFIDENTIALITY CONSIDERATIONS INCLUDING DATA ACCESS AND MANAGEMENT**

For this research, only the direct healthcare team has access to participant's medical records. All collected data will be stored on NHS computers. Manual files will be kept safe within a locked cupboard in a coded room in the hospital office.

The manual files of this study including completed consent forms, questionnaires and pro forma will be kept in a locked cupboard of a coded room in the ENT outpatient department in Queen's Hospital, where medical notes are kept. Only the healthcare team within the department has access to the room.

All electronic data will be password protected and stored on a NHS computer in the ENT outpatients department in Queen's Hospital under personal logins of the research team. Therefore, no one else apart from the direct research team and the health care team will have access to the data.

Personal data will be regarded as strictly confidential. This study will comply with the Data Protection Act 1998 and Caldicott Principles. Action will be taken to ensure research team who will be handling the patient identifiable information are made fully aware of their responsibilities and obligations to respect patient confidentiality. All research team members are required to adhere to Trust/ University codes of conduct.

The confidentiality is ensured through anonymization of data. The Trial register will allocate a Trial Number (e.g. SN001) which will be the only data associated with the patient collected data. Presentation of results will not include any subject identifiable details. Written reports of the study will include only anonymized data.

Throughout the study, only the direct health care team who are also the research team members, which includes the Chief Investigator, [name] will have access to the participants' personal data during the study.

Local research NHS Trust R&D personnel may require access to study records for the purpose of inspection and/or audit. Patient will be asked to consent to this on the consent form.

The data generated will be analyzed within Queen's Hospital, Romford. Only anonymized data will be available outside the hospital.

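### The sponsor may judge causality on its own, but no stated route brings it a serious adverse event that was first judged unrelated

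*Protocol*

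**What the plan says.** Section 15 of the Protocol, under Safety reporting, defines adverse reactions to include "All adverse events judged by either the reporting investigator or the sponsor as having a reasonable causal relationship to the intervention". The wording is either/or, so the sponsor's view is sufficient without the investigator's.

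The general recording rule in the same place is "All Adverse Events and Reactions will be logged in data sheet or reported to CI and have cause analysis and assessment performed". It names the Chief Investigator (CI) but not the sponsor.

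The Serious Adverse Events subsection opens with the rule that SAEs "considered to be 'related' and 'unexpected' will be reported to the sponsor within 24 hours of learning of the event"; the same sentence gives 15 days for the REC. After defining a serious event, the subsection sets out the REC criterion again, on its own: "SAEs will be reported to the REC where in the opinion of the Chief Investigator the event was serious and", followed by the two conditions, related and unexpected.

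Safety is a secondary endpoint in Section 6: "Assess safety of device (record and investigate adverse events, oral status and monitor device integrity through use". The Safety part of the Section 9 data analysis adds "Any side effects or adverse events to be recorded in research record sheets and will be collated for assessment", without saying who assesses or when.

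**The concern.** The two rules do not fit together. The definition gives the sponsor a causality judgement that counts by itself. Such a judgement makes a difference only when the investigator has said that an event is unrelated, because otherwise the event is already an adverse reaction. Yet the SAE rule makes a finding of relatedness a condition for telling the sponsor at all.

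What is at stake is oversight of the most important events. The study follows one treated group of 50 with no control arm, so whether a serious event is attributed to the device rests on case-by-case judgement. If a site judges a hospitalisation unrelated, the protocol states no way for the second party named in its own definition to look at it.

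**Working it through.** No arithmetic applies: the point concerns a reporting pathway, and the plan gives no figure to reproduce. The check has two parts.

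**1. Each class of SAE against both rules.** The definition turns on causality only; expectedness plays no part in it.

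| Site's first judgement | Stated route to the sponsor | Already an adverse reaction? | Could the sponsor's causality view change that? |
|---|---|---|---|
| Related, unexpected | Yes, 24 hours | Yes | No |
| Related, expected | None stated | Yes | No |
| Unrelated, unexpected | None stated | No | Yes |
| Unrelated, expected | None stated | No | Yes |

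The one row with a route is a row where the sponsor's causality view adds nothing to the classification. The two rows where it could add something have no route.

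**2. Search for another route.** Each other place that routes events or data, or that names the sponsor as recipient, was read for a path that an SAE judged unrelated could take.

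- Section 15, Safety reporting: all events go to a data sheet or to the CI. Non-serious events go into the study documents, with follow-up by the research team. The sponsor is not named as recipient.
- Section 9, Safety: events are collated for assessment, with no assessor, recipient or date.
- Section 15, Device Defects: a faulty device goes back to the sponsor. This moves hardware, not SAE reports.
- Section 15, Protocol compliance: accidental deviations go to the CI and the sponsor at once, without a filter. This does not cover SAEs, but it shows that the protocol can send a whole class of event to the sponsor when it means to.
- Section 16: "only the direct healthcare team has access to participant's medical records", and only anonymized data are available outside the hospital. No SAE listing to the sponsor and no date for one is stated.

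Result: no stated route exists for an SAE judged unrelated.

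One gap in the text should be noted. The opening sentence of the SAE subsection does not say who does the considering; the CI is named only for the REC report. This does not rescue the rule, since the sponsor cannot be the one to judge events that it has not yet received.

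**The case against.** The strongest reply is that a definition is not a procedure. The adverse reaction definition sets no deadline for the sponsor's view and does not promise sponsor review of each event. The 24-hour rule says which SAEs are expedited; it does not say that the others are withheld. The sponsor could judge causality later from collated or anonymized data. It is true that no deadline is set and that later transfer is possible. But no such transfer is stated, so the sponsor's role depends on something the protocol does not provide for.

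Several stronger readings are tempting, and the documents do not support them.

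- A reader might infer that such an SAE can never reach the sponsor, or that it would be hidden. The text supports only that no route is stated. Every event is recorded at site and collated, and nothing suggests intent. Nor does the text call the sponsor's judgement independent; it says either/or.
- A reader might infer that the definition also fails for SAEs judged related but expected. It does not: those are adverse reactions on the investigator's judgement alone.
- A reader might want to measure the defect by how far an upper confidence limit for related SAEs among 50 participants moves when one event is reclassified. That shows the effect of changing a count by one. It does not show that the reporting route changes the count, and an SAE called unrelated would still appear in the safety data under that label.

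It can also be said that the risk is small. Section 14 reports no significant adverse events in 27 pilot patients who used the device twice daily, double the use planned here. The sponsor funds the study and supplied the protocol's author, while Section 27 describes the CI as independent, so nothing shows that sponsor review would correct a site's error. These points limit the importance of the concern. They do not remove the conflict, because it is the protocol itself that gives the sponsor a say. Finally, the shared filter may have been chosen on purpose; the text does not tell. Even so, the two sentences would need reconciling.

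**Conclusion.** The concern holds in a limited form. The causality definition gives weight to a sponsor judgement that the SAE rule gives the sponsor no stated opportunity to make, in exactly the cases where it could matter: SAEs first judged unrelated. The size is structural, two of the four classes in the table, and no numerical effect on the safety endpoint can be derived from the documents. SAEs may well be rare here, so this is a correction that should be made, not a threat to the trial's conclusions.

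The conclusion assumes that the opening sentence of the SAE subsection is the complete rule for reporting SAEs to the sponsor, and that Appendix 6, which is not shown and is cited only as the reporting form, adds no wider rule.

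**What to change.** Reconcile the adverse reaction definition with the SAE subsection of Section 15. Rewrite the opening sentence of that subsection so that every SAE is reported to the sponsor within the existing 24 hours, whatever its relatedness or expectedness. Require both the investigator's and the sponsor's causality assessments to be recorded. Keep the related-and-unexpected filter for the 15-day REC report only, where it is already stated.

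The contradiction itself concerns only SAEs judged unrelated. Including those judged related but expected keeps the rule free of any prior classification at site.

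Removing or explaining the sponsor's causality role in the definition would also make the text consistent, but removing it would give up the second assessment.

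The cost of the preferred change is about one sentence and a few extra SAE forms in a 50-participant, low-risk device study. It alters a reporting pathway only and touches no treatment or clinical management rule.

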#### Device Defects

Should an issue arise with the device, either mechanical or software related, participants are advised to contact the study team for troubleshooting advice. Should this occur during a therapy session, participants will be told to discontinue use immediately. If the error cannot be fixed through guided troubleshooting, the device will be replaced (at no cost to the participant). The defective device will be returned to the sponsor and sent to the manufacturer to undertake root cause analysis.

### Protocol compliance

Any accidental protocol deviations that occur will be documented and reported to the Chief Investigator and Sponsor immediately.

## **16. PRIVACY AND CONFIDENTIALITY CONSIDERATIONS INCLUDING DATA ACCESS AND MANAGEMENT**

For this research, only the direct healthcare team has access to participant's medical records. All collected data will be stored on NHS computers. Manual files will be kept safe within a locked cupboard in a coded room in the hospital office.

The manual files of this study including completed consent forms, questionnaires and pro forma will be kept in a locked cupboard of a coded room in the ENT outpatient department in Queen's Hospital, where medical notes are kept. Only the healthcare team within the department has access to the room.

All electronic data will be password protected and stored on a NHS computer in the ENT outpatients department in Queen's Hospital under personal logins of the research team. Therefore, no one else apart from the direct research team and the health care team will have access to the data.

Personal data will be regarded as strictly confidential. This study will comply with the Data Protection Act 1998 and Caldicott Principles. Action will be taken to ensure research team who will be handling the patient identifiable information are made fully aware of their responsibilities and obligations to respect patient confidentiality. All research team members are required to adhere to Trust/ University codes of conduct.

The confidentiality is ensured through anonymization of data. The Trial register will allocate a Trial Number (e.g. SN001) which will be the only data associated with the patient collected data. Presentation of results will not include any subject identifiable details. Written reports of the study will include only anonymized data.

Throughout the study, only the direct health care team who are also the research team members, which includes the Chief Investigator, [name] will have access to the participants' personal data during the study.

Local research NHS Trust R&D personnel may require access to study records for the purpose of inspection and/or audit. Patient will be asked to consent to this on the consent form.

The data generated will be analyzed within Queen's Hospital, Romford. Only anonymized data will be available outside the hospital.

## **17. POTENTIAL BENEFITS**

It is anticipated that the participant will experience improvement in snoring and sleep quality. They can continue to use the device if they choose to after the completion of the study and can participate in on going Post Market Surveillance. They can also be considered for other treatment modalities post completion of trial if appropriate.

## **18. RISK/BENEFIT RATIO**

Due to the low risk nature and transient use of the device there is minimal risk to participants in this study. This device is the only one of its kind that aims to combat the cause of snoring, rather than merely treating the symptom, therefore we feel the benefits far out way the risks.

## **19. EXPENSE TO PARTICIPANT**

There will be no cost to the subject for participating in this study. All the tests and procedures that will be done for this research will be paid for by study funds.

#### **20. COMPENSATION FOR PARTICIPATION**

Participants will be reimbursed for their time and any travel costs with a flat fee of £500.

**23. FUNDING SUPPORT FOR THIS STUDY**

SnooZeal

**24. BIOLOGICAL MATERIALS TRANSFER AGREEMENT**

NA

**25. INVESTIGATIONAL DRUG FACT SHEET AND IND/IDE HOLDER**

NA

**26. IMPACT ON STAFF**

NA

**27. CONFLICT OF INTEREST**

The CI and the research team do not have any financial interests or other conflicts related to this study.

This protocol was written by [name], who is an expert from SnooZeal Ltd. (sponsor).

The protocol has been reviewed by the Chief investigator, [name], who is an independent expert in the field of Sleep Surgery based at the institution of the study.

